7. SAFETY ASSESSMENTS

Threats to Individual Privacy and Data Confidentiality: To minimize risk to participant privacy, all study procedures are conducted in private testing rooms by qualified study personnel and the collection of sensitive information is limited to the minimum necessary to conduct the necessary screening and testing. To minimize risk to participant confidentiality, we will use secure web-based applications (i.e., REDCap) to collect and manage participant information and all data will be stored with unique identification codes such that no personal identifying information will be available in the study files. All data collection forms are electronic Case Report Forms (eCRF). As source documents, all forms are signed or electronically verified and dated by a study staff member. In case of interruption of internet connectivity during data collection, participants will complete a paper version of the eCRF and the Study Coordinator or Research Assistant will transfer all data from the paper forms to the database. Every 2-weeks a Research Assistant will perform a quality assurance check by comparing data entered into the database from paper-based forms. All paper data collection forms will be kept in locked file cabinets located in locked testing rooms.

Voluntary Reaching Task: Bending of the trunk could possibly aggravate current low back pain symptoms; however, these reaching tasks have been chosen because they mimic everyday activities and are within the available range of motion of individuals with low back pain. The reaching tasks minimize potential risks to the participant in that they do not require any lifting; thus, spine loads are minimal. Risk is further minimized because we inform all participants that they are free to stop at any time if they find the procedure too uncomfortable. We have been conducting this reaching protocol with back pain participants for more than a decade and we have never had any incidents of injury or sustained aggravation of back pain symptoms.

Virtual Reality Game Play: Consistent with our Phase I trial, prior to testing participants will be fully informed of the game procedures, including information on the available rewards for performance. The movements required during video game play will be very similar to those required to perform the reaching tasks and will be within the available range of motion of individuals with low back pain. The game play

minimizes potential risks to the participant in that they do not require any lifting; thus, spine loads are minimal. We further minimize risk by informing the participants that they are free to stop at any time if they find the procedure too uncomfortable. Finally, each session will begin with the participant starting with the most basic movement task to encourage success and to allow for the adaption of movement patterns while reducing the risk of exacerbating back pain symptoms.

Some participants could feel nauseated from being in the virtual reality environment, but this is minimized by having precise synchronization of motion of the headset and the graphics presented to the participant. Care is also taken to avoid rapid changes in the visual scenes that can induce motion sickness. Finally, we are pre-screening our applicants to ensure they are not highly susceptible to motion sickness.

There is a risk of falling as vision of the real world is fully occluded by the virtual reality headset. Risk of falling is minimized by having the participant first stand in the testing area and then put on the headset. None of the virtual reality activities require steps to be taken; in fact, we will instruct participants to move their feet as little as possible. Further, the headset will be removed while the participant is still in the testing environment; hence, at no time will participants be ambulatory while their real world vision is obstructed. Additionally, the testing area is an open space with a level surface, minimizing the risk of injury if a participant should fall. Two research staff members will conduct every appointment which allows one to run the software and the other to monitor the study subject.

In keeping with Virginia Commonwealth University Institutional Review Board and US Department of Health and Human Services, Office for Human Research Protections requirements, all study personnel who interact with participants or have access to research data will maintain valid certification of training in the protection of human research participants.

7.1 Specification of Safety Parameters

At each visit the study staff will use the Adverse Event Log to ask the study participants if they have had any change in general health since the last visit. If fever or unexplained weight loss is reported, suggesting systemic infection / disease may be causing their low back pain, the clinician will do a basic physical exam and specifically assess for the possibility they have other systemic illness. They will be advised to seek medical care and research participation may be delayed, temporarily discontinued, or permanently suspended at the discretion of the examining clinician and in consultation with the Medical Directors if needed.

Before each treatment the study staff will use the Contraindications Form to inquire about change in back related signs indicative of increased severity of symptoms. Specifically if they have any new symptoms such as weakness, numbness, or difficulty walking. If the study participant reports yes on any of these items the clinician will do a basic physical exam and assess neurological function by checking myotomes, dermatomes, and reflexes to determine whether the study participant now presents with hard neurological signs (e.g., loss of motor function, significant changes in reflexes), or symptoms of other systemic disease. If the participant does present with hard neurological signs or serious systemic disease, they will be encouraged to seek consultation with their personal physician, and they will be excluded from further participation from the study.

All negative changes in health status other than back pain will be recorded as

Adverse Events, logged, and reported per requirements of the Virginia Commonwealth University IRB and NIH. In the case of dismissal from the protocol for the above stated reasons, the Medical Safety Committee will meet to determine whether the AE was caused by the intervention (Definite, Probable, Possible, Unknown) and an adverse event report will be filed according to the specific requirements of the Virginia Commonwealth University IRB and NIH.

Adverse events will be entered directly into RedCap™, an electronic data management system and assessed twice monthly by the unmasked study coordinator using Tables 4, 5, and 6 located in Appendix A. Adverse events will be recorded and these will be monitored at each study visit to be entered by the RAs. The study coordinator will routinely assess recruitment, participant status, upcoming visits, and outstanding assessments. All Adverse Events will be assessed, classified, and reported according to Appendix A.

7.2 Methods and Timing for Assessing, Recording, and Analyzing Safety Parameters

All Adverse Events will be reported to the Study Coordinator who will complete an Adverse Event Form and collaborate with study staff involved in the AE. If applicable, the Medical Director will review the AE and determine the Common Terminology Criteria for Adverse Events (CTCAE) scale. The Study Coordinator then compiles masked AE reports for the PIs to review. Twice monthly, adverse events and serious adverse events will be assessed by the unblinded study coordinator. Potential unanticipated side effects of the interventions will be monitored at each study visit and entered by a research assistant into the database. A tracking report will be developed as part of the database to allow the coordinator to assess recruitment, participant status, upcoming visits, and outstanding assessments. Annually, an AE summary report will be generated and provided to the Independent Monitors for review and forwarded to the NICHD. At each periodic review, AEs will be reported to the IRB.

All adverse events with start dates occurring any time after informed consent is obtained until 7 (for non-serious AEs) or 30 days (for SAEs) after the last day of study participation will be recorded. At each study visit, the investigator will inquire about the occurrence of AE/SAEs since the last visit. Events will be followed for outcome information until resolution or stabilization.

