Randomization & Stratification: The study statistician will use the R statistical language to block randomize treatments stratified by sex. Then the study coordinator will assign subjects to the treatment arms.

Masking or Blinding: The principal investigators, the statistician, and members of the data collection team will remain blinded to intervention assignment throughout the duration of the study. They will be given the identifying codes only at the end of the study when it is necessary to interpret the results. The un-blinded study coordinator, who is responsible for scheduling testing and treatment sessions, will serve to receive the study patients and escort them to the various testing and treatments sites to minimize the interaction between patients; however, the study coordinator will not participate in the assessments.

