12. COMMITTEES

Steering Committee: The VIGOR Study Steering Committee, which is charged with the overall governance of study conduct, consists of [name], PT, and [name]. The Steering Committee approves the final protocols and manuals of operations, supervises the overall execution of the trial, generates and approves study policies, considers modifications of the protocol and study operations, and plans and drafts study-related publications. The Steering Committee appoints and charges the subcommittees described below. All major scientific decisions are determined by consensus of the Steering Committee.

Medical Safety Committee: The VIGOR Study Medical Safety Committee, which consists of [name], PT, [name], [name], D.O. and Study Coordinator [name], reviews masked study data related to the overall safety of study participation, develops safety reports for the Data and Safety Monitoring Board, addresses IRB issues (related to participant safety) that may arise, reviews clinical practice-related issues and oversees the clinical safety of all study participants.

Data Safety and Monitoring Board: A Data Safety Monitoring Board (DSMB) that consists of an Independent Monitoring Committee IMC (IMC) monitors all aspects of the study, including those that require access to any blinded data.

Recruitment, Adherence, and Retention Committee: The VIGOR Study Recruitment, Adherence and Retention Committee ([name], PT, [name]., and members of the Study Coordination and Data Collection Team) refines and optimizes protocols and strategies for recruitment, adherence and retention of study participants. The Committee oversees recruitment progress, intervenes in cases of under-recruitment, and reports recruitment progress to the Steering Committee.

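### An unblinded coordinator writes up and assesses all adverse events and sits on the committee that judges causality for events leading to dismissal, so masked causality assessment is not assured

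*Combined protocol and SAP*

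**What the plan says.** All of the following is in the combined protocol and SAP.

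- **Who knows the arm.** Sections 5.2, 6.2.3 and 9.2 describe the study coordinator as un-blinded. Section 9.2 adds: "Then the study coordinator will assign subjects to the treatment arms". The principal investigators, the statistician and the data collection team stay blinded.
- **Who writes up events.** Section 7.2: "All Adverse Events will be reported to the Study Coordinator who will complete an Adverse Event Form". The coordinator then compiles masked reports for the principal investigators.
- **Who assesses events.** Section 7.2: "Twice monthly, adverse events and serious adverse events will be assessed by the unblinded study coordinator". Section 7.1 repeats the duty and names the tool: "assessed twice monthly by the unmasked study coordinator using Tables 4, 5, and 6 located in Appendix A".
- **Who judges causality after a dismissal.** When a participant is dismissed for the reasons listed in Section 7.1, "the Medical Safety Committee will meet to determine whether the AE was caused by the intervention".
- **Who sits on that committee.** The membership sentence in Section 12 ends: "and Study Coordinator [name], reviews masked study data related to the overall safety of study participation".
- **Who judges other events.** Section 7.3 has the principal investigators and co-investigators decide whether an event is serious, unexpected or on-site, and has the clinical investigator assign attribution. Under Section 7.2 the Medical Director sets the CTCAE grade where applicable.

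**The concern.** The design summary calls the trial double-blind and gives safety as one of the things it tests. Sections 6.2 and 7.3 both promise unbiased monitoring of adverse events. The arms differ in how much lumbar flexion the games demand, so anyone who knows the arm can be expected to hold a prior view about where harm will show up.

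A masked report protects against this only if the account in it was also written without knowledge of the arm. Deleting the arm label does not change how an event was described or what was left out. If a person who knows the allocation also takes part in deciding causality, the judgement itself is exposed.

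Relatedness has practical consequences. Section 7.4 uses it to decide which unexpected serious events go to the funder, the Independent Monitoring Committee and the IRB on the shortest timelines. The committee on which the coordinator sits also prepares the safety reports for the Data and Safety Monitoring Board (Section 12).

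**Working it through.** No sample size, rate or test statistic is involved, so there is nothing to recompute. The check traces each step in the handling of an adverse event and asks who acts and whether that person is masked.

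| Step | Who acts | Masked? | Source |
|---|---|---|---|
| Event asked about and entered at visits | Study staff, research assistants | Data collection team is blinded | 7.1, 6.2.3 |
| Adverse event form, all events | Coordinator, with the staff involved | No | 7.2 |
| Twice-monthly assessment | Coordinator | No | 7.1, 7.2 |
| CTCAE grade, where applicable | Medical Director | Not stated | 7.2 |
| Serious, unexpected, on-site | Principal investigators and co-investigators | Principal investigators are; co-investigators not stated separately | 7.3, 6.2.3 |
| Attribution in general | Clinical investigator | Not stated separately | 7.3 |
| Reports to the principal investigators | Compiled by the coordinator | Arm removed, author unmasked | 7.2 |
| Causality after dismissal | Medical Safety Committee, coordinator a member | Data described as masked; one member is not | 7.1, 12 |

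Four results follow.

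1. **Dismissal events: the route is direct.** Section 12 says the committee "reviews masked study data related to the overall safety of study participation", but the person who allocated the participants is one of its members. No passage excuses that member from the causality decision. The events concerned include hard neurological signs and serious systemic disease, which are among the most consequential the trial could see.

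2. **Other events: the route is indirect.** Attribution and classification belong to other roles. They may still rest on a form and a report prepared by someone who knows the arm.

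3. **The coordinator's role is stated inconsistently.** Section 9.2 says, without qualification, that the coordinator takes no part in assessments. Sections 5.2 and 6.2.3 confine that exclusion to clinical outcomes and testing. Sections 7.1 and 7.2 make the coordinator an assessor of adverse events. The wording of Section 9.2 cannot stand beside Sections 7.1 and 7.2.

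4. **There are two causality scales.** Section 7.1 offers definite, probable, possible and unknown. Section 7.3 offers unrelated, unlikely, possible, probable and definite. A committee using the first has no category for an event it believes the intervention did not cause.

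**The case against.** The strongest reply is that the coordinator attributes nothing alone. Section 7.3 gives attribution to the clinical investigator and classification to the investigators. The principal investigators are blinded and see masked reports, the Medical Director grades where applicable, and an Independent Monitoring Committee reviews events. The twice-monthly assessment rests on Appendix A tables that are not in the text available. It may be tabulation, since Section 7.1 also uses the word assess for administrative tracking. The exclusion in Section 9.2 can be read as covering outcome assessments only, as Sections 5.2 and 6.2.3 do.

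Much of this stands, and it rules out several stronger readings that a reader might infer:

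- *That the coordinator, or the committee, decides causality for every event.* The committee's ruling is limited to dismissals under Section 7.1.
- *That muscle or joint complaints pass through the committee.* Section 6.2.6 sends sudden muscle or joint pain to the principal investigator or another study clinician, and Section 7.3 does not count back pain as an adverse event.
- *That nobody else looks at an event before the coordinator.* Section 7.2 has the coordinator work with the staff involved, and Section 7.3 has the study team characterise events within 24 hours.
- *That the stopping decision turns on relatedness.* Section 9.4 refers to excessive serious adverse events and leaves the decision to the Independent Monitoring Committee with the funder. All serious events are reported to the principal investigator whatever their relationship to the study (Section 7.4).
- *That a planned between-arm test of related events would be biased.* Section 9.6 plans none.

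The reply does not answer the committee membership, the missing recusal, the unmasked authorship of every form, or the conflict with Section 9.2. If that exclusion was meant to cover outcomes only, it should say so.

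**Conclusion.** The point holds in a limited form. Direct influence of an unmasked person on causality is shown only for events that lead to dismissal. For all other events the influence is possible but indirect, through the form and the compiled reports. The review of masked data described in Section 12 is not fully masked while the coordinator is a member.

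The size of any bias cannot be estimated. The documents give no adverse event rates, and any illustrative difference between arms would rest on invented rates and on the false premise that the coordinator sets attribution. Nothing here shows that attribution will in fact differ by arm.

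The conclusion rests on two assumptions: that no unseen text, such as Appendix A, provides for recusal or masked completion of the form, and that committee membership carries a part in its decisions. Even if either is wrong, the conflict between Section 9.2 and Sections 7.1 and 7.2, and that between the two causality scales, would still need correcting. The change is worth making because the source of bias is avoidable at little cost in a trial that claims to test safety.

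**What to change.** 1. **Sections 7.1 and 12:** make the coordinator a non-voting administrator of the Medical Safety Committee, who supplies masked documents and is absent when causality is decided.
2. **Sections 7.1 and 7.2:** have an existing staff member who knows neither the arm nor the game settings write the event description. This should not be the person who runs the software at the session, a role described in Section 7. Limit the coordinator to logging, masking and transmission.
3. **Section 7.3:** state that attribution and classification are made from the masked form and recorded before any unmasking needed for urgent care, with no delay to that care. State whether the clinical investigator is blinded.
4. **Reconcile:** Section 9.2 with Sections 7.1 and 7.2 on the coordinator's part in assessments, and the causality scale in Section 7.1 with the one in Section 7.3.

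The cost is protocol wording and a small shift of workload to staff already on the study. The practical constraint is finding someone at or near each visit who has not seen the game settings; the protocol should name that role.

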7.3 Adverse Events and Serious Adverse Events

Adverse events: A structured safety monitoring system will be established to both assure real-time participant care and unbiased monitoring of adverse events (AE). For ongoing participant safety, events will be assessed by the PIs and co-investigators to determine if they are Serious, Unexpected, and/or On-site. If so, an event evaluation form will be completed that will include a description of the event, a classification of seriousness, assessment of potential relationship to the intervention, assessment of need for change in the consent or the study activities, a summary of known prior health issues, event outcome, and a classification of the main organ system involved. (See Protection of Humans Subjects for definitions of adverse events).

Adverse Events include any reaction, side effect, or other untoward medical event, regardless of the relationship to the study intervention. For ongoing participant

safety, any adverse events will be characterized within 24 hours by the study team to determine if it was Non-series/Serious, Unexpected/Expected, and Off-site/On-site.

Non-serious adverse events will be defined as conditions that may be unpleasant and bothersome to the participant (e.g., mild nausea) that do not require discontinuing the study intervention or components of the intervention. All adverse events will be documented for review by the Independent Monitoring Committee (IMC) and reported to the IRB. Serious events includes any event that is 1) life threatening, 2) may result in prolonged, permanent, or severe disability, 3) may worsen a pre-existing condition, or 4) requires inpatient hospitalization or surgical procedure, or a treatment to prevent a serious event. All serious adverse events will require immediate notification of a Physician, 24 hour notification of the IRB, and an assessment of the implications for the continuation of the study and/or modification of the consent form.

Unexpected adverse events are defined as events that are not listed in the consent form. Monitoring for unexpected serious adverse events attributable to the intervention is the responsibility of the investigators. Specific reporting and review requirements are defined for unexpected events, so that, if an unexpected event is found to be related to the intervention, the protocol and consent can be modified.

We will utilize the NCI Common Terminology Criteria for adverse Events which are a descriptive terminology that can be utilized for Adverse Event (AE) reporting and provides a grading (severity) scale for each AE. AEs will be labeled according to severity, which is based on their impact on the patient.

Attribution: An assessment of the relationship between the AE and the intervention will be performed using the NCI guidelines which do not define an AE as necessarily “caused by a therapeutic intervention”, after naming and grading the event, the clinical investigator will assign an attribution to the AE as unrelated, unlikely, possible, probable, or definite.

Note that back pain is not considered an adverse event within this research.

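### Worsening back pain is excluded from adverse-event recording without a qualifier, although it is a named risk and can meet the protocol's own seriousness criteria

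*Combined protocol and SAP*

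**What the plan says.** **Exclusion.** Section 7.1 states "All negative changes in health status other than back pain will be recorded as" adverse events. Section 7.3 ends with "Note that back pain is not considered an adverse event within this research". Neither sentence is conditioned on severity, seriousness or relationship to the intervention.

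**Named risk.** Section 7 says of the reaching task that "Bending of the trunk could possibly aggravate current low back pain symptoms". Of gameplay, it describes starting each session with the easiest movements as a way of "reducing the risk of exacerbating back pain symptoms".

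**Seriousness.** Section 7.3 begins its list with "Serious events includes any event that is 1) life threatening". The list goes on to events that "may worsen a pre-existing condition" and to those needing inpatient hospitalization or a surgical procedure. Ongoing low back pain is an inclusion criterion (Section 4.1), so every participant has it as a pre-existing condition.

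**Use of the safety data.** The independent monitors receive an annual adverse-event summary (Section 7.2). The study-level stopping criterion in Section 9.4 is illustrated by an excess of serious adverse events. Section 9.4 also plans no interim analysis of outcome data.

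**Pain as an outcome.** Section 9.6 models pain at pre-treatment and at 1, 6, 12, 24 and 48 weeks. Pain is also rated during treatment (Sections 6.1 and 6.2.4), but no analysis of those ratings is stated.

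**The concern.** The trial has a stated safety purpose (Précis, Design and Outcomes). The most obvious harm of an intervention that makes people with chronic back pain bend further is that their back hurts more. The two arms differ in exactly that exposure, so a difference in exacerbations between arms is plausible. If the exclusion is followed literally, this named harm is missing from the safety data. If it is transient, it is missing from the efficacy analysis as well. Staff who meet a back-pain exacerbation that leads to hospitalization have two sentences in Section 7.3 that point in different directions.

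**Working it through.** **Step 1: does the exclusion cover worsening?** The sentence in Section 7.3 says only back pain and could be taken to mean the baseline complaint. Section 7.1 removes that reading, because it exempts back pain from the negative changes that are recorded. A negative change in back pain is worsening.

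**Step 2: where do the sentences conflict?**

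| Event | Seriousness list, Section 7.3 | Exclusion, Sections 7.1 and 7.3 |
|---|---|---|
| Ordinary fluctuation of back pain | Not clearly covered | Not an adverse event |
| Exacerbation meeting a seriousness criterion, e.g. hospitalization | Serious | Not an adverse event |

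Only the second row is a direct conflict.

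**Step 3: do other records turn worsening into an adverse event?**
- Section 7.1 has a "Contraindications Form to inquire about change in back related signs indicative of increased severity of symptoms". The exclusion from the study and the report that may follow depend on hard neurological signs or serious systemic disease, not on worse pain alone. The form is not listed in Section 6.1 or 6.2.4.
- Section 6.2 describes a health screen before each game session that asks about changes in back pain. It falls under Medical History, which Section 6.1 schedules only at Visit 0.
- Section 6.2.6 covers sudden-onset muscle or joint pain, with session termination, assessment and possible withdrawal. It does not say that the episode is recorded as an adverse event.
- Section 5.3 records concomitant pain management at each visit, with no stated safety use.

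**Step 4: how long is the period with no planned analysis?**
- Nominal: Visit 2 (first session, week 1) to Visit 19 (single session, week 9) spans 8 × 7 = 56 days. Section 6.1.1 puts Visit 20 seven days later: 56 + 7 = 63 days.
- Limit: Section 5.4 allows 9 weeks + 30 days, so 63 + 30 = 93 days. Visit 20 may fall 7 + 3 = 10 days later: 93 + 10 = 103 days.
- Of the six model time points in Section 9.6, none falls within this period.

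**Step 5: which pain data already exist there?** There are 3 × 3 + 3 × 2 + 3 × 1 = 18 treatment visits, each with a current-pain rating. The 7-day and 24-hour ratings are scheduled at the first visit of each week in Section 6.1 (9 visits), but at every treatment visit in Section 6.2.4 (18 visits).

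**Step 6: contrast between arms.** Section 5.1 sets experimental targets at up to 60 degrees of lumbar motion and control targets at 15: 60 − 15 = 45 degrees, or 60/15 = 4-fold, before the 5–15% target adjustment.

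**The case against.** The strongest reply is that pain is a co-primary outcome in a population selected for pain, so excluding it from adverse events is a deliberate design choice. The closing sentence of Section 7.3 can be read as an express exception to the list above it. The seriousness item on pre-existing conditions can also be read as meaning some other event, such as a fall, that worsens the back. Much of this stands, and it is why the conflict is confined to back pain that itself meets a seriousness criterion. It does not explain why a serious exacerbation should go unrecorded, and the outcome analysis does not cover the treatment period.

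A reader might infer that worsening is unmonitored. The documents do not support that. Sections 5.3, 6.2, 6.2.6 and 7.1 provide participant-level steps. Section 7.4 requires unanticipated problems to be reported. Section 7.6 brings difficult situations to the Independent Monitoring Committee. That committee reviews risk against benefit and may recommend modifying or ending the study (Section 7.6), and it may access blinded data (Section 12). Nor is all worsening lost to analysis: pain that persists to Visit 20 is compared by arm (Section 9.6), and outcomes are sought after early discontinuation (Sections 6.2.6 and 8).

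Definitions may also sit elsewhere. Section 7.3 says "See Protection of Humans Subjects for definitions of adverse events", Section 7.1 refers to Appendix A, and Section 7.6 to a Data Safety and Monitoring Plan. None of these is in the available document, and any of them may hold a qualifier.

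Prior experience is reassuring: Section 2.1 reports no exacerbation in Phase I, and Section 7 reports no sustained aggravation from the reaching protocol. Phase I, however, covered 3 sessions against 18 here (18/3 = 6-fold).

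**Conclusion.** The point holds in a limited form and should be corrected. As written, back-pain worsening is outside adverse-event recording without qualification. On the literal text it would therefore not enter the annual summary or count toward the serious-event criterion in Section 9.4. The direct contradiction is limited to exacerbations that meet a seriousness criterion. The analysis gap is limited to worsening that resolves before Visit 20, a period of about 63 days nominally and up to about 103 at the limits. The nominal figure assumes that the first and last sessions fall on the same weekday; the upper figure takes the stated maximum intervention length and the latest Visit 20.

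The number of events affected cannot be estimated, because the documents give no exacerbation rate. It would go too far to infer that harm is occurring, that oversight could not act on it, or that every flare-up is a missed serious event. The conclusion also depends on the definitions outside the available document containing no qualifier.

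**What to change.** 1. Reconcile the risk statements in Section 7, the recording rule in Section 7.1 and the definitions in Section 7.3 with each other and with Appendix A, the human-subjects definitions and the monitoring plan. The result should make clear whether and how back-pain worsening that meets the protocol's own seriousness criteria is recorded and reported. No clinical threshold is proposed.
2. At final analysis, add a descriptive by-arm table of treatment-period change from baseline in the pain ratings, and of sessions terminated or participants withdrawn for pain (Section 6.2.6). First reconcile Sections 6.1 and 6.2.4 on when the 7-day and 24-hour ratings are taken.

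The cost is protocol wording, one table, and logging of the reason and pain site for each stopped session or withdrawal. No additional participant assessments are needed. The table is descriptive and cannot by itself establish or exclude a difference between arms. Closed interim by-arm reports to the monitoring committee are optional and not needed for this fix. If they are considered, by-arm counts from a screen that asks about back-pain change would come close to an interim look at a co-primary outcome, which Section 9.4 does not plan.
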